9.2.3 Medical History

Medical history will be coded by using the Medical Dictionary for Regulatory Activities (MedDRA). For the FAS, medical history will be summarized descriptively by system organ class (SOC) and preferred term (PT). The corresponding data listing will also be provided.

In addition, the number of subjects reported to have had positive cultures for respiratory pathogens within the 2 years prior to screening (i.e., answered yes on the respiratory microbiology form) will be summarized for the FAS. The corresponding data listing will be provided.

9.2.4 Prior and Concomitant Medications

Medications will be coded using the World Health Organization Drug Dictionary (WHODrug) and categorized as follows:

Prior medication: any medication that was administered during the 56 days before the first dose of study drug.

Concomitant medication: medication continued or newly received during the TE period.

Post-treatment medication: medication continued or newly received after the TE period.

A given medication may be classified as follows: prior, concomitant, post-treatment, both prior and concomitant, both concomitant and post-treatment, or prior, concomitant, and

post-treatment.

If a medication has a completely missing or partially missing start/stop date and if it cannot be determined whether it was taken before the first dose date of study drug, concomitantly, or after the TE period, it will be classified as prior, concomitant, and post-treatment. Details for imputing missing or partial start and/or stop dates of medication are described in [Appendix B](#).

Prior medications and concomitant medications will be summarized descriptively for FAS using frequency tables by: 1) treatment group and overall, preferred name (PN); and 2) treatment group and overall, Anatomical Therapeutic Chemical class (ATC) level 1, ATC level 2, and PN.

Post-treatment medications will be listed in all medication listing.

9.2.5 Study Drug Exposure

Duration of study drug exposure (in days) will be calculated as: last dose date of study drug – first dose date of study drug, regardless of study drug interruption.

Study drug exposure (in weeks) will be summarized descriptively by the number of subjects (n), mean, SD, median, min, and max. It will also be summarized by interval: ≤ 1 week, >1 to ≤ 2 weeks, >2 to ≤ 4 weeks, >4 to ≤ 8 weeks, >8 to ≤ 12 weeks, >12 to ≤ 16 weeks, >16 to ≤ 20 weeks, >20 to ≤ 24 weeks, and >24 weeks using counts and percentages. Additionally, the total study drug exposure, defined as the sum total of the study drug exposure across all subjects (in patient-weeks and patient-years), will be provided.

Exposure summaries will be based on the Safety Set and presented by treatment group and overall.

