[figure not shown]
The total study duration is approximately 32 weeks (4 weeks for the Screening Period, 24 weeks for the Treatment Period, and 4 weeks for the Safety Follow-up Period).

Study Design

This is a Phase 3, randomized, placebo-controlled, double-blind, parallel group study. Subjects 6 years of age and older with a qualifying non-F508del ELX/TEZ/IVA-responsive CFTR mutation and no exclusionary mutations may be eligible for enrollment. Qualifying ELX/TEZ/IVA-responsive mutations can be categorized as minimal function (MF)-like and residual function (RF)-like. MF-like mutations have a clinical phenotype without evidence of residual CFTR function. RF-like mutations result in residual CFTR function. Exclusionary mutations are indicated for IVA in the EU label regardless of the mutation on the second allele.

Subjects will be randomized 2:1 (ELX/TEZ/IVA group: placebo group). Randomization will be stratified based on ppFEV₁ determined during the Screening Period (<70 versus ≥70), age at the Screening Visit (<18 years old versus ≥18 years old) and *CFTR* genotype (contains ≥1 RF-like mutation versus does not contain an RF-like mutation).

Figure 2-1 Study VX21-445-124 Design

The ELX/TEZ/IVA dose regimen will be based on the subject's age and weight on Day 1 as shown in Table 2-1; Subjects will receive this dose regimen throughout the Treatment Period, regardless of changes in age or weight.

Table 2-1 Treatment Period Dosages

Treatment Group Subject Age			
Weight	ELX Dosage	TEZ Dosage	IVA Dosage
ELX/TEZ/IVA			
≥12 years			
All weights	$200~\mathrm{mg}~\mathrm{qd}$	$100 \mathrm{\ mg\ qd}$	$150 \mathrm{\ mg\ q} 12\mathrm{h}$
≥6 to <12 years			
≥30 kg	200 mg qd	100 mg qd	$150 \mathrm{\ mg\ q} 12\mathrm{h}$
<30 kg	100 mg qd	50 mg qd	75 mg q12h
Placebo			
All ages and all weights	0 mg	0 mg	0 mg

ELX: elexacaftor; IVA: ivacaftor; q12h: every 12 hours; qd: once daily; TEZ: tezacaftor

ELX/TEZ/IVA will be administered as 2 FDC tablets in the morning and a single IVA monotherapy tablet in the evening regardless of dosing regimen.

Assessments

Efficacy and PD assessments: spirometry, CFQ-R, sweat chloride, weight, height, and PEx

Safety assessments: AEs, clinical laboratory assessments, ECGs, vital signs, pulse oximetry, physical examinations, and ophthalmologic examinations (for subjects <18 years of age on the date of informed consent)

PK assessments: Plasma PK concentrations of ELX, TEZ, IVA, and their relevant metabolites

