8.2 Full Analysis Set

The **Full Analysis Set** (FAS) will include all randomized subjects who carry the intended mutation and received at least 1 dose of study drug. The FAS will be used to summarize subject demographics and baseline characteristics, and for analyses of all efficacy endpoints in which subjects will be analyzed according to their randomized treatment group, unless otherwise specified.

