8.3 Safety Set

The **Safety Set** will include all subjects who received at least 1 dose of study drug. The Safety Set will be used for all safety analyses in which subjects will be analyzed according to the treatment they received, unless otherwise specified. If a subject received study drug from both

the placebo group and the treatment group, the subject will be analyzed in the Safety Set of the treatment group.

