9.2.6 Study Drug Compliance

Study drug compliance will be summarized by treatment group and overall based on the FAS.

Study drug compliance will be calculated as: $100 \times [1 - (\text{total number of days of study drug interruption}) / (\text{duration of study drug exposure in days})]$. A study drug interruption on a given day is defined as an interruption of any study drug on that day. A study drug interruption that continues through the end of the study participation (i.e., subject does not resume study drug before the end of the study participation) will not be included in the compliance calculation.

Percentage of study drug compliance will be summarized descriptively by the number of subjects (n), mean, SD, median, min, and max and based on the FAS, and presented by treatment group and overall. It will also be summarized in categories: $<80\%$ and $\geq 80\%$ using frequency tables.

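### SAP 9.2.5 omits the + 1 day from study drug exposure, so exposure is one day short where dose dates are known and compliance (9.2.6) is undefined for a subject dosed on a single day

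*SAP*

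**What the plan says.** SAP 9.2.5 (Study Drug Exposure) defines duration in days as the last dose date minus the "first dose date of study drug, regardless of study drug interruption". The result is reported in weeks, in weekly categories from ≤1 week to >24 weeks, and as total patient-weeks and patient-years, all on the Safety Set.

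SAP 9.2.6 (Study Drug Compliance) is 100 × [1 − interruption days / exposure], where the denominator is the "duration of study drug exposure in days". Interruptions are counted by calendar day: "A study drug interruption on a given day is defined as an interruption of any study drug on that day". An interruption that is never resumed is left out, since the rule says that it "subject does not resume study drug before the end of the study participation) will not be included in the compliance calculation". Compliance is also tabulated as <80% and ≥80%, on the FAS.

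Both populations admit a subject with a single dose. The FAS is "all randomized subjects who carry the intended mutation and received at least 1 dose of study drug", and the Safety Set "will include all subjects who received at least 1 dose of study drug". No rule covers a denominator of zero, and neither document adds the missing day elsewhere.

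**The concern.** Subtracting one calendar date from another gives the number of steps between them, which is one fewer than the number of days in the span. In the exposure table this is a uniform loss of one day. In the compliance formula it also creates a mismatch: the numerator counts whole days, while the denominator counts steps between days. The mismatch hardly matters in a long exposure. It matters in a short one, and for a subject whose only dosing day is Day 1 the formula cannot be evaluated.

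At stake are the descriptive exposure and compliance tables, mainly the entries for subjects who stop early.

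**Working it through.** **Inputs**
- First dose is Day 1 and the Week 24 target is Day 169 (SAP Appendix A, Table 12-1).
- A completer's last dose is the evening before the Week 24 Visit (Protocol 9.6), so Day 168 on schedule.
- The planned duration is "24 weeks for the Treatment Period" (Protocol synopsis), which is 24 × 7 = 168 days.
- Planned N is 270 (SAP 7.2).

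**Day-numbering check.** Target day = 7 × week + 1 gives 15, 29, 57, 113 and 169 for Day 15 (week 2) and Weeks 4, 8, 16 and 24. All five match Table 12-1, so Day 1 to Day 168 is 168 dosing days.

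**Exposure, SAP formula (last − first) against inclusive count (last − first + 1)**

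| Last dose | SAP, days | Inclusive, days | Shortfall |
|---|---|---|---|
| Day 168 | 167 (23.86 weeks) | 168 (24.00 weeks) | 1/168 = 0.6% |
| Day 8 | 7 | 8 | 1/8 = 12.5% |
| Day 2 | 1 | 2 | 1/2 = 50% |
| Day 1 | 0 | 1 | 100% |

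**Total, if all 270 subjects complete on schedule with known dates**
- SAP formula: 270 × 167 = 45,090 days = 123.45 patient-years.
- Inclusive: 270 × 168 = 45,360 days = 124.19 patient-years.
- Difference: 270 days = 270/7 = 38.6 patient-weeks = 270/365.25 = 0.74 patient-years.

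**Exposure categories.** A subject moves only when the SAP figure falls exactly on a cut-point.
- Last dose Day 8: 7 days (≤1 week) against 8 days (>1 to ≤2 weeks).
- Last dose Day 169: 168 days (>20 to ≤24 weeks) against 169 days (>24 weeks). This can occur because the Week 24 Visit has a ±5-day window (Protocol Table 3-2).
- Last dose Day 168: >20 to ≤24 weeks under both rules.

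**Compliance = 100 × (1 − interruption days / exposure days)**
- Dosed on Day 1 only: the denominator is 0 and the value is undefined. With + 1 and no counted interruption it is 100 × (1 − 0/1) = 100%.
- Last dose Day 10, 2 interruption days: 1 − 2/9 = 77.8% against 1 − 2/10 = 80.0%. The subject changes category at the 80% cut.
- Dosed Day 1, interrupted Days 2 to 10, last dose Day 11: 1 − 9/10 = 10% against 1 − 9/11 = 18%. The subject is below 80% under both rules.
- Last dose Day 168, 10 interruption days: 1 − 10/167 = 94.01% against 1 − 10/168 = 94.05%.
- Last dose Day 168, near the cut: 33 interruption days give 80.2% against 80.4%, and 34 days give 79.6% against 79.8%. The category does not change.
- More than one dosing day and no counted interruption: 100% under both rules.

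**Imputed last dose dates (SAP Appendix A).** A missing or partial last dose date is imputed from the ETT visit date, the last visit before Safety Follow-up, or the last recorded administration date. For a completer imputed from an on-schedule Week 24 Visit, last − first = 169 − 1 = 168 days, which is already the inclusive count. Adding 1 would give 169.

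**The case against.** The formula is a pre-stated definition, applied in the same way to both arms, and it contradicts no printed figure. Read as elapsed time it is defensible: from the morning of Day 1 to the evening of Day 168 is about 167.5 days, so the two counts are each about half a day off. Protocol 9.1.2 describes the Treatment Period as lasting only approximately 24 weeks, and no text says that exposure must equal 168 days. This makes the exposure table a matter of convention. It does not rescue compliance, where whole days are divided by the difference, and it does not deal with the zero denominator.

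A reader might infer that every exposure and compliance figure is wrong. The documents do not support that:
- Subjects with an imputed last dose date may not be understated at all. An ETT visit can fall 3 weeks or more after the last dose (Protocol 9.1.4), which would overstate exposure.
- Compliance is unaffected for multi-day subjects with no counted interruption, and unresumed interruptions are excluded.
- Most subjects stay in the same exposure category.

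A reader might also infer an effect on efficacy or safety results. None follows. Adverse events are summarised as counts and percentages of subjects (SAP 9.4.1), the treatment-emergent period is set by dates (SAP 9.1), and the exacerbation model uses its own analysis period as offset (SAP 9.3.2.1 and 9.3.2.2).

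Finally, the documents do not say how many single-day subjects to expect. There may be none.

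**Conclusion.** The point holds as a minor definitional error in descriptive output. Exposure is short by exactly one day for each subject with known first and last dose dates. The relative loss is largest for the earliest discontinuers, but the absolute loss is the same for all. The total of 0.74 patient-years is an upper figure: it assumes that all 270 subjects are dosed and have known dates. The comparison with about 124 patient-years further assumes that all complete on schedule. The relative effect should be nearly equal in the two arms.

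The defect in compliance is the firmer part. The value is undefined when first and last dose dates coincide, slightly low when interruptions are counted, and able to cross the 80% cut in short exposures. One single-day subject is enough to leave a value in the FAS compliance table that cannot be computed.

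**What to change.** In SAP 9.2.5, define exposure as last dose date − first dose date + 1 day. Section 9.2.6 already refers to that duration, so its denominator follows; say so explicitly. This removes the zero denominator and puts both parts of the ratio in days.

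Where the last dose date is imputed from a visit date under Appendix A, check that it does not already include the extra day. A completer's Week 24 Visit date is the day after the last dose, so the day should not be added a second time there.

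The cost is one term in a formula, one line of programming and a sentence on imputed dates. No new data are needed. SAP section 4 allows the change by amendment before data lock; after that it would be noted in the clinical study report.

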9.2.6 Study Drug Compliance

Study drug compliance will be summarized by treatment group and overall based on the FAS.

Study drug compliance will be calculated as: $100 \times [1 - (\text{total number of days of study drug interruption}) / (\text{duration of study drug exposure in days})]$. A study drug interruption on a given day is defined as an interruption of any study drug on that day. A study drug interruption that continues through the end of the study participation (i.e., subject does not resume study drug before the end of the study participation) will not be included in the compliance calculation.

Percentage of study drug compliance will be summarized descriptively by the number of subjects (n), mean, SD, median, min, and max and based on the FAS, and presented by treatment group and overall. It will also be summarized in categories: $<80\%$ and $\geq 80\%$ using frequency tables.

9.2.7 Important Protocol Deviations

An important protocol deviation (IPD) is a deviation that may significantly affect the completeness, accuracy, or reliability of the study data or that may significantly affect a subject's rights, safety, or well-being. A protocol deviation review team will categorize IPDs according to the Protocol Deviation Plan during the study.

IPDs will be provided in an individual subject data listing. A summary table of IPDs based on the FAS will also be provided.

9.3 Efficacy Analysis

All efficacy analyses described in this section will be based on the FAS, unless otherwise specified.

9.3.1 Analysis of Primary Efficacy Endpoint

9.3.1.1 Definition of Variables

The primary efficacy variable is the absolute change in ppFEV₁ from baseline through Week 24. Percent predicted FEV₁ is the ratio of FEV₁ (L) and predicted FEV₁ (L), expressed as a percentage. See [Appendix C](#) for more details.

9.3.1.2 Primary Analysis

The primary analysis will be performed using a MMRM with change from baseline at Day 15, Week 4, Week 8, Week 16, and Week 24 as the dependent variable. The model will include treatment group, visit, and treatment by visit interaction as fixed effects, with continuous baseline ppFEV₁, age at screening (<18 versus \geq 18 years of age) and mutation group (contains \geq 1 RF-like mutation versus does not contain an RF-like mutation) as covariates. The model will be estimated using restricted maximum likelihood. Denominator degrees of freedom for the *F*-test for fixed effects will be estimated using the Kenward-Roger approximation². An unstructured covariance structure will be used to model the within-subject errors. If the model estimation does not converge, a compound symmetry covariance structure will be used instead. Conditional on the observed data and covariates, missing data will be assumed to be missing at random.

The primary result obtained from the model will be the estimated treatment difference through Week 24, defined as the averaged treatment effects estimated at Week 4, Week 8, Week 16, and Week 24. The adjusted means with 2-sided 95% CIs and 2-sided *P* value will be provided. Furthermore, the treatment difference at each post-baseline visit obtained from the model will also be provided.

The estimated within group change from baseline and treatment difference at each post-baseline visit, obtained from the model, will be provided. The estimated within group change and its SE at each post-baseline visit will also be plotted by treatment group. In addition, the post-baseline raw values and the absolute change from baseline at each post-baseline visit will be summarized descriptively (n, mean, SD, median, minimum, and maximum).

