7.2 Sample Size and Power

Approximately 270 subjects will be enrolled and randomized (2:1) to the ELX/TEZ/IVA arm or the placebo arm.

The primary endpoint is the absolute change from baseline in ppFEV₁ through Week 24. The primary null hypothesis to be tested is that the mean absolute change from baseline in ppFEV₁ through Week 24 is the same for the ELX/TEZ/IVA and placebo treatment groups. The null hypothesis will be tested at a 2-sided significance level of 0.05.

Assuming a within group SD of 9 percentage points and a 10% dropout rate at Week 24, a total sample size of 270 subjects (180 subjects in the ELX/TEZ/IVA group and 90 subjects in placebo group) will have approximately 90% power to detect a difference of 4.0 percentage points for the mean absolute change from baseline in ppFEV₁ through Week 24 between the 2 treatment groups, based on a 2-sided 2-sample *t*-test at a significance level of 0.05.

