7.3 Randomization

Subjects will be randomized 2:1 (ELX/TEZ/IVA group: placebo group). Randomization will be stratified based on ppFEV₁ determined during the Screening Period (<70 versus \geq 70), age at the Screening Visit (<18 years old versus \geq 18 years old) and *CFTR* mutation group (contains \geq 1 RF-like mutation versus does not contain an RF-like mutation).

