9.1 General Considerations

The Schedule of Assessments is provided in Section 3 of the CSP. The precision standards for reporting safety and efficacy variables are provided in an internal Biometrics document that specifies the programming rules including the precision for derived variables.

Continuous variables will be summarized using the following descriptive summary statistics: the number of subjects (n), mean, SD, median, min, and max.

Categorical variables will be summarized using counts and percentages. Percentages will be presented to 1 decimal place.

Baseline value, unless otherwise specified, will be defined as the most recent non-missing measurement (scheduled or unscheduled) collected before the first dose of study drug in the Treatment Period. For ECGs, the baseline value will be defined as the most recent pretreatment measurement (or the average of triplicate measurements, if the most recent pretreatment measurement is obtained in triplicate) before the first dose of study drug.

Absolute change from baseline will be calculated as post-baseline value - baseline value.

Relative change from baseline will be calculated as (post-baseline value - baseline value)/baseline value.

The **Treatment Emergent (TE) Period** will include the time from the first dose date of study drug to 28 days after the last dose of the study drug or to the completion of study participation date, whichever occurs first.

Unscheduled visits: Unscheduled visit measurements will be included in analysis as follows:

- 1) In scheduled visit windows per specified visit windowing rules
- 2) In the derivation of baseline and last on-treatment measurements
- 3) In the derivation of max and min during TE period, and maximum and minimum change from baseline values during TE period for safety analyses
- 4) In individual subject data listings as appropriate

Visit windowing rules: The analysis visit windows for protocol-defined visits are provided in [Appendix A](#).

Incomplete/missing data will not be imputed, unless otherwise specified.

Outliers: No formal statistical analyses will be performed to detect or remedy the presence of statistical outliers, unless otherwise specified.

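### Screening ppFEV₁ enters no efficacy model; adding it as a second covariate in the primary MMRM would give a modest gain in precision at almost no cost

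*SAP*

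**What the plan says.** SAP 7.3 names three stratification factors, the first being lung function: "Randomization will be stratified based on ppFEV₁ determined during the Screening Period", split at 70. The others are age group and CFTR mutation group.

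SAP 9.3.1.2 carries age group and mutation group into the primary model, with one ppFEV₁ term: "The model will include treatment group, visit, and treatment by visit interaction as fixed effects, with continuous baseline ppFEV₁, age at screening". Under SAP 9.1, baseline is "the most recent non-missing measurement (scheduled or unscheduled) collected before the first dose of study drug in the Treatment Period". Protocol Table 3-2 schedules spirometry before dosing on Day 1, so baseline is normally the Day 1 reading.

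A screening FEV₁ between 40% and 100% of predicted is required for entry (Protocol 8.1, criterion 6). That value is used for eligibility, for stratification and in the baseline table (SAP 9.2.2), but in no efficacy model. SAP 9.3.1.3 plans no supportive analysis of the primary endpoint that might use it.

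Protocol 12.3.3.1 leaves additional covariates to the SAP, so the protocol already permits another one.

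**The concern.** The dependent variable is change from baseline, averaged over Weeks 4, 8, 16 and 24. The same baseline reading is subtracted at all four visits, so averaging over visits does not reduce its noise. Adjusting for that reading alone helps little, because one reading cannot separate a subject's usual level from that day's deviation. A second reading taken before randomisation can do so in part.

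At stake is the width of the primary confidence interval, and some power for the test that gates the secondary endpoints (Protocol 12.3.3.4). The endpoint, the estimand and the sample size would not change.

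**Working it through.** **Inputs from the plan (SAP 7.2).** "Assuming a within group SD of 9 percentage points and a 10% dropout rate at Week 24"; "180 subjects in the ELX/TEZ/IVA group and 90 subjects in placebo group"; a 4.0-point difference; power "based on a 2-sided 2-sample *t*-test at a significance level of 0.05".

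**Inputs assumed (not in the documents).** Visit-to-visit SD σe of 3 to 6 points. SD of a single baseline reading of 14 to 18 points. Extra screening noise σx of 0, 3 or 5 points for mixed bronchodilator state.

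**Step 1. Reproduce the plan's figure.** After 10% dropout, 162 and 81 subjects remain. The standard error is 9 × √(1/162 + 1/81) = 9 × 0.1361 = 1.225, and 4/1.225 = 3.27. The noncentral t gives power 0.902 and the normal approximation 0.904. The stated figure of about 90% holds, with no covariate gain assumed.

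**Step 2. Model.** Let u be a subject's usual pre-treatment level and d the subject's own deviation from the mean treatment-period change.

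- Baseline = u + noise (variance σe²).
- Screening = u + independent noise (variance σe² + σx²).
- Mean of the four post-dose visits = u + d + noise (variance σe²/4).

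The variance of the averaged change is σd² + σe²/4 + σe² = σd² + 1.25σe². I set this to 9² = 81, so σd² = 81 − 1.25σe². The between-subject variance is σu² = (baseline SD)² − σe².

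**Step 3. Residual variance.**

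- Baseline only: V1 = σd² + σe²/4 + 1/(1/σu² + 1/σe²)
- Baseline plus screening: V2 = σd² + σe²/4 + 1/(1/σu² + 1/σe² + 1/(σe² + σx²))

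**Step 4. Example: σe = 5, baseline SD 18, σx = 0.** σd² = 81 − 31.25 = 49.75, σe²/4 = 6.25 and σu² = 324 − 25 = 299.

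- V1 = 56 + 1/(1/299 + 1/25) = 56 + 23.07 = 79.07 (SD 8.89)
- V2 = 56 + 1/(1/299 + 2/25) = 56 + 12.00 = 68.00 (SD 8.25)
- Reduction: 1 − 68.00/79.07 = 14.0%

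Adjusting for baseline alone takes the variance only from 81 to 79.

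**Step 5. Range, baseline SD 18 (power by noncentral t, 162 v 81, 4 points).**

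| σe | σx | V1 | V2 | Variance cut | Power |
|---|---|---|---|---|---|
| 3 | 0 | 80.75 | 76.44 | 5.3% | 0.903 → 0.918 |
| 3 | 5 | 80.75 | 78.96 | 2.2% | 0.903 → 0.909 |
| 4 | 0 | 80.21 | 72.80 | 9.2% | 0.905 → 0.929 |
| 4 | 5 | 80.21 | 76.09 | 5.1% | 0.905 → 0.919 |
| 5 | 0 | 79.07 | 68.00 | 14.0% | 0.909 → 0.944 |
| 5 | 5 | 79.07 | 71.79 | 9.2% | 0.909 → 0.933 |
| 6 | 0 | 77.00 | 61.94 | 19.6% | 0.916 → 0.961 |
| 6 | 5 | 77.00 | 65.99 | 14.3% | 0.916 → 0.950 |

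With baseline SD 14 the cuts run from 2.1% to 17.8%. If the plan's 9 is instead the SD of change at a single visit, they run from 2% to 30%.

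**Step 6. On the scale of the result.** The 95% half-width is about 1.96 × 0.1361 × residual SD. For like-for-like readings it goes from 2.40 to 2.33 points at σe = 3, and from 2.37 to 2.20 at σe = 5.

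**Step 7. Simulation check.** Each setting had 3,000 trials of 243 subjects, with screening truncated to 40–100. The averaged change was regressed on treatment and baseline, with and without screening. The estimate stayed at about 4.0 throughout. Its variance fell by 6% to 15% with like-for-like readings (σe 3 to 6), and by 8% to 12% with 5 extra points of screening noise (σe 5 and 6).

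**The case against.** A reader might infer that stratifying on screening ppFEV₁ and modelling baseline ppFEV₁ is a mismatch that invalidates or underpowers the primary analysis. The documents do not support that. A continuous baseline value is an accepted replacement for a two-level stratum of the same quantity, and the power claim rests on an unadjusted test.

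A reader might also take the screening reading as an independent repeat of Day 1, held on every subject and never used. That is too strong, for four reasons:

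- Screening spirometry may be done before or after bronchodilator; later visits should be pre-bronchodilator (Protocol 11.4.1).
- Day 1 is timed to the inhaled-antibiotic cycle (Protocol 9.5), with no matching rule for screening. The screening window can be extended for a CFTR-modulator washout, and screening tests can be repeated (Protocol 9.1.1.1 and 9.1.1.3).
- If Day 1 is missing, the baseline rule in SAP 9.1 makes the screening value the baseline, and that subject has no second reading.
- The value is unused only in the efficacy models.

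These points shrink the gain. They do not bias the comparison, because the value is measured before randomisation.

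The strongest objection is to size. Every percentage above rests on SDs that the documents do not supply, and at the low end power moves by less than one percentage point. That objection stands, and it limits the point to an inexpensive improvement.

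**Conclusion.** The point holds as a gain in efficiency. The primary analysis is valid and adequately powered as written. Adding screening ppFEV₁ would lower the variance of the treatment difference in every scenario examined: by about 2% to 20% over the assumed ranges, and by about 5% to 14% for like-for-like readings with visit-to-visit SD 3 to 5. In that narrower case, power at 4 points goes from about 0.90–0.91 to 0.92–0.945.

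The result assumes that screening and Day 1 noise are independent and that 9 is the SD of the averaged change. Any drift between the two visits acts like extra screening noise and moves the gain towards the low end.

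**What to change.** Before data lock and unblinding, amend SAP 9.3.1.2 as follows:

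- Add continuous screening ppFEV₁ as a separate covariate beside continuous baseline ppFEV₁. Use the last screening-visit value, derived by the GLI rules in SAP Appendix C. The value must be named, because Protocol 11.4.1 uses the investigator's own assessment for eligibility.
- Keep change from baseline as the dependent variable. Do not average the two readings, since their bronchodilator state may differ.
- Where Day 1 is missing and screening serves as baseline, enter the same value for both terms.
- State whether the term is confined to the ppFEV₁ models. SAP 9.3.2.2 describes the secondary MMRMs only as similar to the primary one, and the calculation here covers ppFEV₁ alone.

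The term carries automatically into the subgroup MMRMs (SAP 9.3.1.5) and the MMRM fitted after imputation (Appendix D), because both reuse the primary model. The Appendix D imputation draws contain no covariates and do not change.

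The cost is one degree of freedom and a short SAP amendment; no new data are needed. The likely gain can be sized while blinded from the spread of the screening-to-Day 1 differences. The restriction on the study team's access to spirometry (Protocol 10.7.1) covers only results after the first dose. If many screening readings are post-bronchodilator, the gain is smaller.
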